Assuming that the true incidence of adverse events related to decreased sympathetic function in CLBP subjects enrolled in A4091059 and this study is 6%, when 170 subjects are enrolled in this study, these adverse events are expected to occur in 4 to 10 subjects (4%-9%) in this study at a probability of $\geq 80\%$, and in 6 to 14 subjects (4%-8%) in combined A4091059 and this study at a probability of $\geq 80\%$.

Main Safety and Efficacy Analysis

The efficacy and safety population will be the ITT population, defined as all randomized subjects who received SC investigational product (either tanezumab or matching placebo).

Adverse events, concomitant medications, laboratory safety tests, physical and neurological examinations, vital signs, electrocardiogram (ECG), and the anti-drug antibody test will be collected for each subject during the study according to the Schedule of Assessments. Standard safety reporting tables will summarize and list the safety data.

The incidence of subjects with any of the adjudication outcomes of rapidly progressive osteoarthritis (type-1 and type-2), subchondral insufficiency fracture (or SPONK), primary osteonecrosis, or pathological fracture will be shown by number of subjects treated and subject years of exposure (treatment plus follow-up periods), for individual treatment groups and differences between tanezumab treatment groups and the celecoxib treatment group. The risk ratio and risk difference with 95% confidence intervals will be calculated for the comparisons of each tanezumab group versus the celecoxib group.

For the efficacy endpoints, summary statistics will be shown by timepoints and by treatment group. For the continuous endpoints and the binary endpoints, the difference with 95% confidence intervals between tanezumab treatment groups and the celecoxib treatment group will be calculated, but no inferential testing will be performed.

DATA MONITORING COMMITTEE

An independent, external Data Monitoring Committee (E-DMC) has been instituted for the tanezumab clinical program. This committee will be composed of at least one rheumatologist, neurologist, statistician, and epidemiologist. The E-DMC will review unblinded safety data including (but not limited to) adverse events and serious adverse events on a regular basis throughout the trial. The E-DMC will have written operating procedures and a Charter, including a specific description of the scope of their responsibilities.

SCHEDULE OF ACTIVITIES

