- The NIS is the sum of scores over all 37 items from both the Left and Right side. The change from baseline to each post-baseline visit in the NIS will be summarized. The change from Baseline to each study visit, and to Worst (largest) change from Baseline (over all post-Baseline visits) will be summarized.
- The neurological consultation data will be summarized all subjects, and for subjects with adverse events of abnormal peripheral sensation, which are described in the Neurological Examination Section (Section 7.3.9). The “conclusion from the neurological examination” data will be summarized for each timepoint, and as well as a summary of the final assessment over all neurological examinations for each subject.
- The incidence of subjects with any of the joint safety adjudication outcomes of rapidly progressive osteoarthritis (type-1 and type-2), subchondral insufficiency fracture (or SPONK), primary osteonecrosis, or pathological fracture will be shown by number of subjects treated and subject years of exposure (treatment plus follow-up periods), for individual treatment groups and differences between tanezumab treatment groups and the celecoxib treatment group. The risk ratio and risk difference with 95% Confidence intervals will be calculated for the comparisons of each tanezumab group versus the celecoxib group. The time to each event will be summarized, and (where there are sufficient numbers of subjects) Kaplan-Meier estimates of the time to event will be produced.
- The incidence of subjects with any of the joint safety adjudication outcomes of rapidly progressive osteoarthritis (type-2), subchondral insufficiency fracture (or SPONK), primary osteonecrosis, or pathological fracture will be analyzed as described above. In addition the same analysis will be performed for the individual events of all-cause Total Joint Replacements, and adjudicated outcomes of rapidly progressive osteoarthritis (type 1, type 2 and both types 1 and 2 combined), subchondral insufficiency fracture (or SPONK), primary osteonecrosis and pathological fracture.

- A listing of the subjects who develop anti-tanezumab antibodies after treatment for each dose, and the proportion of subjects who develop anti-tanezumab will be summarized for each dose.
- The PK profile will be examined for subjects with anti-tanezumab antibodies.
- Individual subjects with positive ADA results will be evaluated for potential ADA impact on the individual's efficacy and safety profile.

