5.2.4. Analyses for Time to Event Data

Survival curve estimates (time to 1st, 2nd, 5th, 10th and 25th percentiles, and minimum and maximum values) and a plot of the time to event will be shown using the Kaplan-Meier estimates. Only discontinuation up to the end of treatment period (Week 56 visit or early discontinuation) will be used in this analysis.

Any subject who discontinues for any other reason than lack of efficacy prior to the Week 56 visit uses censoring at the time of discontinuation. Imputation of time to event for completed subjects or discontinued subjects (for any reason) after the Week 56 visit uses censoring at the Week 56 visit time point.

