6.1.1. Safety Measures: Adverse Events

Pfizer standard safety data presentations will be made for adverse event data.

The details of Tier-1, Tier-2 and Tier-3 AEs are described in [Section 3.5.1](#).

Treatment-emergent adverse events within Tier-1 will be summarized. The combined Tier-1 adverse events, but not each adverse event will be summarized using Risk Differences between each tanezumab group and celecoxib, together with 95% CI and p-value, using exact methods. Treatment-emergent adverse events within Tier-2 will be summarized using Risk Differences between each tanezumab group and celecoxib, together with 95% CI, using exact methods. There will be no multiplicity adjustment for these significance tests. These tables will be produced for the comparisons of tanezumab 5mg versus celecoxib and tanezumab 10mg versus celecoxib.

The following footnote will be used in the Tier-1 AE tables: “P-values and confidence interval are not adjusted for multiplicity and should be used for screening purpose only. 95% CIs are provided to help gauge the precision of the estimates for Risk Difference.” Similarly the following footnote will be used in the Tier-2 AE tables: “Confidence intervals are not adjusted for multiplicity and should be used for screening purpose only. 95% Confidence intervals are provided to help gauge the precision of the estimates for Risk Difference.”

It should be recognized that most studies are not designed to reliably demonstrate a causal relationship between the use of a pharmaceutical product and an adverse event or a group of adverse events. Except for select events in unique situations, studies do not employ formal adjudication procedures for the purpose of event classification. As such, safety analysis is generally considered as an exploratory analysis and its purpose is to generate hypotheses for further investigation. The 3-tier approach facilitates this exploratory analysis.

Pfizer standard safety data presentations will be made for demography data, concomitant medications, discontinuation data, adverse event data, laboratory test data, vital sign data and ECG data.

The non-standard safety tables as described in [Section 3.5.1](#) will also be summarized. The details are described below.

Summary of AEs, Incidence of AEs, Incidence of AEs leading to discontinuation and summary of Serious AEs will be shown for the whole study period (including the safety follow-up period) will be created.

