6.1.6. Safety Measures: Joint Safety Adjudication Outcomes and Total Joint Replacements

Adjudication outcomes to be summarized include rapidly progressive osteoarthritis (type-1 only), rapidly progressive osteoarthritis (type-2 only), rapidly progressive osteoarthritis (type-1 or type-2 combined), subchondral insufficiency fracture, primary osteonecrosis, pathological fracture, normal progression of OA and other joint outcomes. The incidence of subjects with any of the adjudication outcomes of rapidly progressive osteoarthritis (type-1 or type-2), subchondral insufficiency fracture, primary osteonecrosis, or pathological fracture will also be summarized. Total joint replacement (TJR) will also be summarized. Output will show the number and percentage with 95% CI (exact confidence interval) of subjects for each outcome. In addition, subject years of exposure for individual treatment group and exposure adjusted event rates (number of subjects with an adjudicated joint safety event divided by exposure) of each outcome (with 95% CI) will also be shown. For each outcome, association with TJR, affected joint(s), and baseline Kellgren-Lawrence Grade of affected joint will be summarized. Number of TJRs during study, study period of first TJR occurrence, number of only elective TJR, number of joints with TJR prior to study, location of TJR prior to study will also be summarized.

Events will be included in summaries if they occur up to the end of the safety follow-up period or 26 weeks (planned duration of the follow-up period + 2 weeks) after the end of the treatment period, whichever is later.

For the joint safety event analyses, the observation period is defined as the time from first SC dose to study completion or discontinuation for subjects who did not have an event, or time from first SC dose to the earliest event for subjects who did have at least one event.

Reporting of total joint replacement events including surgery will be described in a separate Statistical Analysis Plan that will cover patients in this subset from Studies 1059, 1061 and 1063. Corresponding data from Studies 1056, 1057 and 1058 will be reported under study 1064. Summary listings for the data from the 1063 substudy will be part of the 1063 study CSR as there are <10 total joint replacement events expected in the substudy.

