6.2.1. Average Low Back Pain Intensity (LBPI) Score

Change from Baseline to Weeks 1, 2, 4, 8, 12, 16, 24, 32, 40, 48, 56 and 64 in average LBPI score.

For each treatment and each timepoint assessed, the endpoint will be summarized along with 95% CIs. Handling of missing data is described in [Section 5.3](#).

The ANCOVA model for change from baseline of aLBPI up to week 56 described in [section 5.2.2](#) will also be conducted. The plot of LS mean (+/- SE) for change from baseline up to week 56 will also be prepared.

LBPI data obtained after the early termination visit and considered as off-treatment will be shown in the listing and not be included in any summaries and analyses.

Cumulative distribution of percent change from Baseline in average LBPI score to Weeks 16, 24 and 56.

The cumulative aLBPI response at Weeks 16, 24 and 56 using response definitions from a reduction of >0% to =100% (in steps of 10%) will be summarized, using observed data, mixed BOCF/LOCF, and also LOCF and BOCF imputation for aLBPI (see [Section 5.3](#)).

Imputation with BOCF for subjects with missing data at that timepoint will lead to the subjects being assessed as non-responders for the response endpoint.

Plots of cumulative distribution of percent change from Baseline in average LBPI score to Week 16 and Week 56 (mixed BOCF/LOCF) will be created.

Response as defined by a $\geq 30\%$, $\geq 50\%$, $\geq 70\%$ and a $\geq 90\%$ reduction from Baseline in weekly average LBPI score derived from the subject diary at Weeks 16, 24, 40 and 56.

For each treatment and each timepoint assessed, the number and percentage of subjects in each response category endpoint will be summarized along with 95% CIs. Treatment differences of proportion of responder between each tanezumab treatment group versus celecoxib group will be estimated with 95% CI of Agresti-Caffo method. These analyses use observed data, mixed BOCF/LOCF, and BOCF and LOCF for missing data. The use of BOCF for missing data implies subjects with missing data are included in the analysis as non-responders. Similarly the use of LOCF in the case where subjects have no post-Baseline data (and Baseline would be carried forward) again implies those subjects are included in the analysis as non-responders.

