7.2. Interim Analyses and Summaries

Events relating to joint safety, including reported Osteonecrosis or events leading to Total Joint Replacement will be reviewed by a blinded expert adjudication panel. A stopping rule relating to a set of adjudicated outcomes has been defined, and is described below.

If the blinded Adjudication Committee identifies adjudicated events of rapidly progressive osteoarthritis type 2, subchondral insufficiency fractures, primary osteonecrosis, or pathological fracture, occurring at a rate that could trigger the protocol-based stopping criteria, an urgent, ad hoc assessment of the events will be made by the E-DMC.

The protocol (or treatment group) stopping rule has three components; the difference in the number of subjects with an adjudicated joint safety event, the exposure-adjusted risk difference (RD) and the exposure adjusted risk ratio (RR) between each tanezumab treatment group and celecoxib treatment group. The exposure-adjusted RD will be calculated as the difference in the ratios of the number of subjects with an adjudicated joint safety event divided by exposure (patient-years) between each tanezumab group and the comparator group. The exposure-adjusted RR will be similarly calculated using the ratio of exposure adjusted event rates (number of subjects with an adjudicated joint safety event divided by exposure) for each tanezumab group relative to the comparator group. The exposure will be calculated as the combined treatment and follow-up periods.

CCI and the RR is and the difference in the number of subjects with adjudicated events joint safety event for any tanezumab treatment group versus the comparator treatment group, the protocol-based stopping rule will be triggered. If the protocol-based stopping rule is triggered, the E-DMC will formulate a recommendation whether it is safe to continue dosing in some or all treatment groups or whether the study should be terminated completely. This decision will be made by Pfizer in consultation with the E-DMC.

Separate sets of dosing suspension rules for specified Serious Adverse Events and events consistent with Hy's Law are described in Sections 9.6.1.1 and 9.6.1.2 of the protocol, respectively.

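### SAP 6.1.6 plans no comparison with celecoxib for the joint-safety outcomes, although protocol 9.2 commits to risk ratios and risk differences with 95% CIs

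*SAP*

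**What the plan says.** Protocol 2.2.1 and SAP 3.1 both list joint-safety adjudication outcomes and total joint replacements (TJR) as primary endpoints.

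For the main adjudicated composite, protocol 9.2 states: "The risk ratio and risk difference with 95% Confidence intervals will be calculated for the comparisons of each tanezumab group versus the celecoxib group". It applies the same analysis to a composite restricted to type-2 rapidly progressive osteoarthritis (RPOA), and then adds: "In addition the same analysis will be performed for the individual events of all-cause Total Joint Replacements", followed in the same sentence by each individual adjudicated outcome. It also asks for a summary of time to each event, with Kaplan-Meier estimates where enough subjects have events. The Protocol Summary repeats the commitment for the main composite: "The risk ratio and risk difference with 95% confidence intervals will be calculated for the comparisons of each tanezumab group versus the celecoxib group".

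SAP 6.1.6 says: "Output will show the number and percentage with 95% CI (exact confidence interval) of subjects for each outcome". It adds subject-years by arm, an exposure-adjusted rate with CI for each outcome, and descriptive breakdowns such as affected joint and baseline Kellgren-Lawrence grade. It names no difference, ratio or time-to-event summary.

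The SAP keeps comparisons with celecoxib elsewhere. In 6.1.1: "Treatment-emergent adverse events within Tier-2 will be summarized using Risk Differences between each tanezumab group and celecoxib, together with 95% CI, using exact methods". In 6.2.1: "Treatment differences of proportion of responder between each tanezumab treatment group versus celecoxib group will be estimated with 95% CI of Agresti-Caffo method".

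**The concern.** Protocol 1.2.7 presents the active control arm as the benchmark for long-term safety, and sections 1.2.4.2 and 1.2.4.5 report a higher RPOA risk with tanezumab than with placebo or active comparator. The joint outcomes are thus where a comparison with celecoxib is most needed, yet the final analysis plan provides none.

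A reader could derive a crude risk difference or ratio from the reported counts. The interval method would then be chosen after the data were seen, and with few events that choice can decide whether zero lies inside the interval. A time-to-event summary could not be rebuilt from per-arm counts.

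**Working it through.** **1. Protocol against SAP**

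| Protocol 9.2 | SAP 6.1.6 | Elsewhere in the SAP |
|---|---|---|
| Incidence by arm, per subject treated and per subject-year | Planned, with CIs | n/a |
| Risk difference (RD) and risk ratio (RR) versus celecoxib, 95% CI | Absent | 5.2.1 gives within-arm rates only. 6.1.1 covers combined Tier-1 terms (five autonomic terms) and common MedDRA terms, not adjudicated outcomes |
| Time to event, Kaplan-Meier if numbers suffice | Absent | 5.2.4 covers discontinuation only: "Only discontinuation up to the end of treatment period (Week 56 visit or early discontinuation) will be used in this analysis" |
| Type-2-only composite | Not listed | Defined in 3.5.6 |

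SAP 7.2 does use an RD and RR for joint events ("The protocol (or treatment group) stopping rule has three components"). Those are triggers for the data monitoring committee. They carry no CI and leave out type-1 RPOA and TJR.

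Protocol 9.2 covers nine endpoints: the main composite; the type-2-only composite; all-cause TJR; RPOA type 1, type 2 and combined; subchondral insufficiency fracture; primary osteonecrosis; and pathological fracture. That makes 9 endpoints x 2 doses x 2 measures = 36 between-arm estimates. SAP 6.1.6 plans none.

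**2. Arm size**

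The plan's figures reproduce: 170/3 = 56.7, 200/3 = 66.7 and 220/3 = 73.3, against the stated 56, 66 and 73 per arm. The documents give no expected rate for the joint composite. Protocol Table 3 classes RPOA as uncommon (below 1%). All event counts below are therefore assumptions.

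**3. What the missing estimate would look like (66 per arm, Newcombe)**

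With Wilson limits (l, u) for each arm and d = p1 - p2:

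- lower = d - sqrt[(p1 - l1)^2 + (u2 - p2)^2]
- upper = d + sqrt[(u1 - p1)^2 + (p2 - l2)^2]

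For 3 versus 1:

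- p1 = 4.55% (Wilson 1.56 to 12.53) and p2 = 1.52% (0.27 to 8.10), so d = 3.03 points.
- lower = 3.03 - sqrt(2.99^2 + 6.58^2) = 3.03 - 7.23 = -4.2
- upper = 3.03 + sqrt(7.99^2 + 1.25^2) = 3.03 + 8.08 = 11.1

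| Tanezumab arm v celecoxib | RD, points | 95% CI |
|---|---|---|
| 1 v 0 | 1.5 | -4.1 to 8.1 |
| 2 v 0 | 3.0 | -2.9 to 10.4 |
| 3 v 1 | 3.0 | -4.2 to 11.1 |
| 4 v 0 | 6.1 | -0.6 to 14.6 |
| 5 v 0 | 7.6 | 0.6 to 16.5 |

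Over the allowed range of arm sizes, 3 versus 1 gives 3.6 (-4.9 to 12.9) at 56 per arm and 2.7 (-3.8 to 10.1) at 73.

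**4. Dependence on the interval method**

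- RD at 4 versus 0: Newcombe -0.6 to 14.6; Miettinen-Nurminen score 0.35 to 14.6; Agresti-Caffo -0.95 to 12.7. Only the score interval excludes zero.
- RD at 5 versus 0: the Newcombe interval excludes zero, but Fisher's exact p is 0.058.
- RR at 3 versus 1 is 3.0. The score interval is 0.44 to 20.8. The log method has SE = sqrt(1/3 - 1/66 + 1 - 1/66) = 1.14, giving 0.3 to 28. The RR is not estimable when celecoxib has no events.

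**5. How likely these counts are**

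For one arm of 66, the probability of 5 or more events is 0.0005, 0.010 and 0.048 at true rates of 1%, 2% and 3%. At 1%, the probability of 4 or more is 0.004 and of 0 or 1 is 0.86.

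**The case against.** **The departure is allowed.** Protocol section 9 and SAP section 2 let the SAP change protocol plans; only major changes to a primary analysis call for an amendment, and SAP 5.1 tests no hypotheses. This stands as far as it goes, and whether the change is major is a judgement. But the RD and RR are estimates rather than tests, and Amendment 2, the current protocol, still promises them.

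**The change was logged.** The version 2 entry cites blinded data review and alignment of analyses across the program, and records that the treatment difference was removed from the general method for binary data (5.2.1). For 6.1.6 it says only that the plan was updated. Version 3 then put the difference back for pain responders, a secondary endpoint, but not for joint outcomes. The rationale is generic and does not explain this omission. The original SAP is not available, so it is unknown whether it held these comparisons.

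**Per-arm exact intervals already bound the risk.** This is partly right. With 66 per arm, the exact upper limits for 1, 2, 4 and 5 events are 8.2%, 10.5%, 14.8% and 16.8%. The RD upper limits against zero celecoxib events are 8.1, 10.4, 14.6 and 16.5 points, so little is added at that end. The lower end differs: 4 of 66 has an exact lower limit of 1.7%, while the Newcombe RD against 0 of 66 reaches -0.6, because the celecoxib rate is itself uncertain (exact upper limit 5.4%).

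**Events may be too few to matter.** This stands in part. Subjects with knee or hip osteoarthritis are largely excluded, so 4 or 5 events in an arm are improbable at a 1% rate, and the Kaplan-Meier condition may not be met. The time-to-event summary itself is not conditional.

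**A separate SAP covers TJR.** It was not available. As described in SAP 6.1.6 and 6.4, it concerns surgery and recovery, and its analysis set (4.3) contains only subjects who had a TJR. That set alone cannot give incidence versus celecoxib.

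**Conclusion.** The point holds and should be fixed. A primary safety endpoint loses the active-control comparison that the protocol specifies, and nothing else in the SAP replaces it in the final analysis. This rests on comparing the texts and does not depend on the assumed event counts.

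What is lost is a pre-specified descriptive estimate, not a test. Its main use would be to state how large an excess over celecoxib cannot be ruled out: about 8 to 11 points at 1 to 3 events per tanezumab arm in the 1 v 0, 2 v 0 and 3 v 1 cases, assuming 66 per arm and Newcombe limits.

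A smaller alignment gap sits alongside. SAP 3.5.6 defines a type-2-only composite and a composite of TJR or any adjudicated outcome, and 6.1.6 lists neither. The first is also a protocol commitment; the second is only an inconsistency within the SAP.

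**What to change.** In SAP 6.1.6:

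- Add RD and RR with 95% CI for 5 mg versus celecoxib and 10 mg versus celecoxib, for every endpoint named in protocol 9.2. Give them both crude and exposure-adjusted, since the protocol presents incidence on both bases.
- Name one interval method that is valid with zero cells (exact or score), and report the RR as not estimable when celecoxib has no events.
- Add the time-to-event summary, with Kaplan-Meier where numbers suffice, using the observation period that 6.1.6 already defines.
- List the type-2-only composite and the TJR-or-any-outcome composite, so that 6.1.6 matches 3.5.6.

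If the comparison was left out on purpose, state the reason in the SAP and amend protocol 9.2 and the Protocol Summary.

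The cost is SAP wording and a few table columns. No new data are needed, because 6.1.6 already requires the counts, subject-years and time to earliest event. The drawback is that with few events the intervals will be wide and the RR will sometimes be missing.

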Subjects who complete the Week 56 visit will be considered to have completed the Double-blind Treatment period and will enter the 24-week Safety Follow-up period. Subjects that have completed the Double-blind Treatment period and have entered the 24-week Safety Follow-up period and complete the Week 80 visit will be considered to have completed the study. Subjects who discontinue study treatment prior to completing the Week 56 visit will not be considered to have completed the Double-blind Treatment Period. Subjects that do not complete the Double-blind Treatment period but who enter and complete the 24-week Early-termination follow-up period will be considered to have completed the study while those subjects who do not complete the 24-week Early-termination follow-up period will not be considered to have completed the study.

For subjects who withdraw from the study, see Section 6.9.1. Every effort should be made to have the subject agree to complete the entire 24-week Early Termination Safety Follow-up.

Details relevant to the study design can be found in Sections 6 and 7 and the SUBSTUDY SCHEDULE OF ACTIVITIES (Appendix 18, Table 7)

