6.4.10. Week 56 Visit-End of Treatment Visit

The subject will return for clinic visits at Week 56 to be assessed for efficacy and safety. Refer to Schedule of Activities [Table 1](#) for the procedures to be performed at the Week 56 Visit.

Radiographic assessment (X-rays) of hips, knees, and shoulders, and any major other joint imaged at Screening or at-risk joint identified during the study period. The X-rays may be obtained within ± 30 days of the Week 56 visit. Radiographs must be sent to the Central Reader for assessment.

At Week 56, subjects will enter the Follow-up Period which lasts until Week 80.

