6.8. Week 80 Visit-End of Study Visit

The subject will return for clinic visits at Week 80 to be assessed for safety. Refer to Schedule of Activities [Table 2](#) for the procedures to be performed at the Week 80 Visit.

Radiographic assessment (X-rays) of hips, knees, and shoulders, and any other major joint imaged at Screening or at-risk joint identified during the study period. The window for the Week 80 X-rays is ± 30 days of the nominal time of the visit but should be obtained as close as possible to the Week 80 visit, and preferably no more than 14 days after the Week 80 visit.

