X-rays of the hips, knees and shoulders (and any other major joint imaged at Screening or identified as at risk during the study) should be performed as soon as possible after the decision to withdraw from the study has been made, provided at least 30 days have passed since the last set of X-rays were collected. The remainder of efficacy and safety assessments should be done at scheduled first visit, which is to occur 8 weeks after the last dose of investigational product (as described in 6.9.1.1).

The site should also schedule the subject for two additional clinic visits. The second visit should be scheduled to occur approximately 16 weeks after the subject's last dose of SC investigational product to collect safety and efficacy data. Once the clinic visit 16-weeks after the last administration of SC investigational product has been completed and final efficacy assessments have been collected, standard of care treatment may be offered to subjects for the remaining 8 weeks of the required Follow-up Period. Standard of care treatment may be initiated as needed and recorded on the concomitant medication CRF. The third and final clinic visit should be scheduled to take place approximately 24-weeks after the subject received the last dose of SC investigational product. That visit, (described in 6.9.1.5), includes repeat X-rays of the hips, knees and shoulders as well as any additional joint that was imaged at Screening or any joint identified as at risk during the study, providing at least 30 days have elapsed since the last radiographs were obtained. The window for obtaining end of study X-rays is 30 days before or 14 days after the nominal time of the visit. Telephone contact will be made with subjects at approximately 12 and 20 weeks following

the last SC dose of investigational product. Every effort should be made to have the subject agree to complete the entire 24 week Early Termination Safety Follow-up described above.

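### The SAP's cut-off for joint-safety events falls before the end of the protocol's permitted window for the final radiograph, so an outcome first seen on a late but in-window film can be left out of a primary safety summary

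*SAP*

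**What the plan says.** **Event limit.** SAP 6.1.6 says: "Events will be included in summaries if they occur up to the end of the safety follow-up period or 26 weeks". The second limb in full is "26 weeks (planned duration of the follow-up period + 2 weeks) after the end of the treatment period, whichever is later". The same section ends observation time at study completion or discontinuation for subjects without an event, and at the earliest event for the others. It does not say which date an event carries (onset, film, central read or adjudication), and it does not date the end of safety follow-up.

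**End of treatment and of follow-up.** Protocol Section 3: "Subjects who complete the Week 56 visit will be considered to have completed the Double-blind Treatment period". Protocol 6.4.10: "At Week 56, subjects will enter the Follow-up Period which lasts until Week 80". Section 3 adds that those who go on to "complete the Week 80 visit will be considered to have completed the study".

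**Final film, Week 80.** Protocol 6.8 sets the window at plus or minus "30 days of the nominal time of the visit but should be obtained as close as possible to the Week 80 visit". The introduction to Section 6 and Section 7.3.8 give the same window. All three places state the 14-day limit only as a preference: "preferably no more than 14 days after the Week 80 visit".

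**Final film, Early Termination Visit 3.** Protocol 6.9: "The window for obtaining end of study X-rays is 30 days before or 14 days after the nominal time of the visit". Protocol 6.9.1.5 instead allows 30 days on either side of the visit, with 14 days after it as a preference.

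**Status.** Joint safety adjudication outcomes are a primary endpoint (Protocol 2.2.1, SAP 3.1).

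**The concern.** The SAP's allowance of two weeks beyond planned follow-up equals the protocol's preferred limit for the Week 80 film. It does not reach the permitted limit of 30 days. A film taken between the two is a valid scheduled assessment, and a suspicious finding on it goes to the Central Reader and the Adjudication Committee. Read literally, the resulting event may still fall outside the incidence and exposure-adjusted tables.

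Week 80 is the last scheduled set of films for subjects who complete treatment, who have the longest exposure. Some joint outcomes are found only because a scheduled film was taken. Any omission lowers the event count in a study whose primary objective is long-term safety.

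**Working it through.** **Inputs**
- Week 56: Day 393, window ±7 days, so Days 386 to 400 (Protocol Table 1).
- Week 80: Day 560, window ±7 days (Protocol Table 2). SAP Appendix 2.1 uses Day 561 as its Week 80 target.
- Week 80 film: nominal visit ±30 days (Protocol Sections 6, 6.8 and 7.3.8).
- Event limit: the later of end of follow-up and 26 weeks after end of treatment (SAP 6.1.6).

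**The SAP's own figure.** 24 weeks of follow-up + 2 weeks = 26 weeks = 182 days. It reproduces.

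**Completers.** Take follow-up as ending at the Week 80 visit.

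Cut-off = max(Week 80 visit day, Week 56 day + 182). Last permitted film = 560 + 30 = Day 590. Gap = 590 − cut-off.

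| Week 56 visit | Cut-off | Last permitted film | Gap |
|---|---|---|---|
| Day 386 | Day 568 | Day 590 | 22 days |
| Day 393 | Day 575 | Day 590 | 15 days |
| Day 400 | Day 582 | Day 590 | 8 days |

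With Day 561 for Week 80, each gap is one day longer.

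**Does taking the later limit close the gap?** The latest in-window Week 80 visit is Day 567 (560 + 7), before all three cut-offs. With Day 561 it is Day 568, which only ties with the earliest. So the follow-up limb never moves the cut-off. The gap closes only if Week 56 falls on Day 408 or later (590 − 182), outside its window.

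**Share of the window.** On target dates, Days 576 to 590 are permitted but past the cut-off: 15 of 61 permitted days, or 25%. This is a share of days, not of films.

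**Early terminators.** Visit 3 is 24 weeks (168 days) after the last SC dose. Let treatment end t days after that dose, so the 26-week limit is t + 182 days after the dose. The visit itself falls at 168 + 7 = 175 days at the latest, so again the follow-up limb does not help.
- Under Protocol 6.9.1.5, the latest film on nominal timing is 168 + 30 = 198 days after the dose. It passes the limit when 198 > t + 182, that is, t < 16.
- Under Protocol 6.9, the latest film is 168 + 14 = 182 days after the dose, which never exceeds t + 182.
- A Week 16 non-responder last dosed at Week 8 has t = 56 and a limit of 238 days, so the film is covered under either window.

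**Scale.** Protocol 9.1 expects 34% to 54% completers. Of 200 subjects that is 68 to 108 with a Week 80 film due. The documents give no distribution of film dates. If 5% to 25% of these films fell after the cut-off (an assumption), that would be 68 × 0.05 = 3.4 to 108 × 0.25 = 27 films. These are films, not events. Protocol Table 3 classes rapidly progressive osteoarthritis as uncommon (0.1% to under 1%). Applying that to the late films gives 3.4 × 0.001 = 0.003 to 27 × 0.01 = 0.27 expected cases over all arms. This is only a rough scale: the table covers one of the outcomes and rests on historic studies. Should one event be lost, it would be 1/66 = 1.5 percentage points in an arm of 66.

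**The case against.** The best counter-argument is that the SAP never says follow-up ends on the Week 80 clinic date. The film is itself a Week 80 procedure (Protocol Table 2 and 6.8). Protocol 6.4 ends the treatment period when the Week 56 procedures are complete. By analogy, follow-up would end when the last Week 80 procedure is done, and a film on Day 590 would carry the limit with it. In addition, the SAP counts events that occur by the limit, and an event dated to earlier symptom onset would be counted. Joint replacements are presumably dated by surgery, so the film window would not affect them. The protocol also asks for films close to the visit, and sites check at Week 76 that they are scheduled. The rule is the same in every arm, and late findings are still adjudicated.

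All of this stands as a limit on the claim. The loss is conditional, and late films should be a minority. It does not remove the conflict, because the text supports the other reading at least as well: the protocol says follow-up lasts until Week 80 and ties study completion to that visit. The SAP chooses neither reading and makes no exception for the final film.

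A reader might infer that only completers can lose events. The documents do not support that: under the wider Visit 3 window, a subject whose treatment ends within 16 days of a dose could also be affected. A reader might also take the 3 to 27 late films above as events lost. That range rests on an assumed late-film rate and counts films.

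**Conclusion.** The SAP's event limit and the protocol's film window do not match. On target dates the gap is 15 days (Days 576 to 590), and it is 8 to 22 days across the Week 56 visit window. An event is omitted only if it is dated at the film and follow-up ends at the Week 80 visit; the SAP leaves both open. For early terminators, omission needs the wider of the two stated film windows and treatment ending soon after a dose.

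The documents do not show that any event will be lost, nor how many. The number is probably small. The direction is certain, since the mismatch can only reduce the count of a primary safety outcome. The choice of window also bears on the rates: between study completion and the 26-week limit, events count while event-free subjects add no observation time.

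**What to change.** In SAP 6.1.6:
1. Include every adjudicated event identified on the protocol-scheduled final radiograph (Week 80 or Early Termination Visit 3) taken within its permitted window. This is the cleaner option because it does not depend on visit timing. The alternative is a longer limit: at least 24 weeks + 30 days = 198 days after end of treatment on nominal timing, and 205 days if Week 56 is on Day 386. (Both take Week 80 as Day 561; with Day 560 each is one day shorter.)
2. State which date defines the event.
3. Run observation time to the same limit for subjects with and without events.

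Separately, reconcile the Early Termination Visit 3 film windows in Protocol 6.9 and 6.9.1.5.

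The cost is a few sentences in the SAP and the alignment of one protocol window. No procedure, visit or data item is added.
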